### **8.3 Assessment of Efficacy**

To assess 30-Day Sustained Abstinence from Smoking (NACQ, 2016) participants are asked the following questions in the Outcome Survey to determine Russell Standard Self- Reported 4-Week Quitter status (West et al., 2005):

1. Have you smoked (even a puff) in the last 30 days?

- a. Yes
- b. No

2. (If yes, this question will appear) Have you smoked (even a puff) in the last 14 days?
  - a. Yes
  - b. No
3. (If yes, this question will appear) Have you smoked (even a puff) in the last 7 days?
  - a. Yes
  - b. No

The Outcome Survey will instruct subjects to submit an exhaled carbon monoxide (CO) reading with the iCO Smokerlyzer they were mailed after participant randomization. iCO Smokerlyzer devices will be programmed to email the exhaled carbon monoxide measurement results to the research coordinator directly.

The primary outcome, 30-day abstinence from smoking, will be assessed via self-report on the outcome survey. Confirmation with the remote CO assessment will be conducted to assess concordance between self-report and remote CO assessment results. Abstinence as per the CO assessment will be defined as an iCO reading of fewer than 7ppm exhaled CO.

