### **11. QUALITY CONTROL AND QUALITY ASSURANCE**

#### **11.1 Data Collection**

Data collection during the 8-week study will occur through the Baseline Survey, Smokerlyzer Confirmation (Day 28), the Outcome Survey at 8 weeks and the iCO Smokerlyzer assessment.

Primary outcome data, including covariates to be included in regression analyses, are acquired via the web-based baseline survey and outcome survey. Data are conveyed via an automated process from the web-based survey into a format matching the study database. Research coordinator is responsible for entering the survey data into the study database within 72 hours of survey completion.

Secondary outcome data: 1) CO readings are automatically conveyed via email by the iCO Smokerlyzer App to the study coordinator, who will enter the result into the database (a numerical value in parts-per-million (ppm; <7 ppm is defined as evidence of cigarette abstinence); 2) self-reported NRT and smoking cessation pharmacotherapy use (including e- cigarette use) will be acquired via the outcome survey.

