### Smokerlyzer instructions for use:

1. Plug the white cord into the Smokerlyzer and into your phone’s headphone jack
2. Take a deep breath and hold it for 15 seconds
3. Exhale into the Smokerlyzer
4. Readings will appear on your phone instantly
5. Results will be explained and charted

Go to this [\[LINK\]](#) for the iCO Smokerlyzer device video instructions ☺

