### **15.16            How to use a Smokerlyzer Video Script**

Hi, I'm [name] from My Digital Study and today I'll be showing you how to use your new Smokerlyzer for the digital smoking cessation study. A Smokerlyzer is a handheld device used to measure the amount of carbon monoxide in your breath. We highly encourage you to use your Smokerlyzer throughout the study to track your progress and motivate you. Regular use of your Smokerlyzer will push you to see your carbon monoxide values drop and ensure that your Smokerlyzer is working properly. While not required, we would really appreciate it if you

submitted your values throughout the study. Doing so allows us to better support you throughout your journey and personalize your experience.

Your kit should come with an ICO Smokerlyzer, a white stereo cord, and a small visual diagram for further instructions.

Start by downloading the free Smokerlyzer app. This can be done by first opening the apple store or google play store on your mobile device. Go to the “search” tab of the store and tap the search bar. Type in “Smokerlyzer.” The Smokerlyzer app should be one the first results. Proceed to download the app.

[cut scene of [name] doing that]

When you open the app, the app will first ask for you preferred language. On the following the app will request a pin code. Your pin code will be on the back of your new Smokerlyzer. Input this pin code to proceed to the next page. Next, the app will ask for your Clinician’s name and email address. Enter “[name]” for the Clinician and “[[contact]](mailto:[contact])” for the email.

The next page will for your name and email address. Please enter your full name and your preferred email address.

[does that]

Now, you’re ready to use your Smokerlyzer. Plug the white cable cord into the Smokerlyzer and then into your phone’s headphone jack.

For those with an iPhone 7 or later, use an adapter to plug the smokerlyzer into your iPhone. One end of the adapter should plug into the other end of the white cable cord and the other end of the adapter should plug directly into the bottom of your iPhone. This adapter should have come with in the box when you purchased your iPhone.

[attaches wires]

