With the app open and ready, select “new breath test.” Turn the volume on your mobile device to the maximum setting. On the top of your screen, you should see “device status: connected” in white font. Wait a few seconds for the program to load. Once loaded, the gray bar on the bottom will turn blue, stating “begin test.”

The program will first ask to take a deep inhalation and hold your breath for 15 seconds. After 15 seconds, the program will instruct you to exhale into the Smokerlyzer. Be sure to completely exhale all the air in your lungs. Readings will appear on your phone instantly.

[[name] holds breath]

After complete exhalation, wait a couple seconds for the program to load. Once loaded, the gray bar on the bottom will turn blue, stating “press to continue.” On the following page, the program will ask two questions about the number of cigarettes you smoke per day and how long you wait

until you smoke your first cigarette of the day. After filling out this information, press “continue.” The next page will provide a brief qualitative analysis of your smoking habits. On the following page, the program ask for a name and email address to share your results with. The name “[name]” and email address “[contact]” should already be appear in this section. If that content does not appear, enter that information manually. Next, select “send email.” A page will slide up displaying your email draft. Select “send” in the top right corner of the page. It is very important that you complete these instructions exactly so that information from your breath tests can be shared with my digital study.

[finish demonstration]

Congratulations, you’ve completed your first Smokerlyzer test.

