This fully-remote study will rely on digital procedures for data collection (e.g., web-based surveys; auto-emailed results of the CO assessment). Use of web-based surveys for primary data collection enables us to ensure the completion of data collected (forms can not be submitted unless complete and incomplete fields can be highlighted for participants). Survey data are conveyed in a format matching the study database for ease of entry into the study database by the research coordinator. The research coordinator will be responsible for entering all survey data into the study database within 72 hours of survey completion. Using these remote, digital procedures nature of the study results in data collection procedures that ensure the integrity of data collected. Validity of self-reported smoking cessation has been established in previous trials. To ensure the validity of the remote CO monitoring, a subsample of the first 50 study completers will be invited to complete the CO monitoring assessment on a live video feed to confirm identity.

Regulatory Issues

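### CO readings are described as automatically e-mailed, but participants see them first and choose whether to send them, so unmonitored readings can be selected and concordance may be biased upward

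*Protocol*

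**What the plan says.** Three places describe transmission without any participant action.

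- Protocol 8.3: "iCO Smokerlyzer devices will be programmed to email the exhaled carbon monoxide measurement results to the research coordinator directly".
- Protocol 11.1, repeated in the SAP under Data Acquisition: "CO readings are automatically conveyed via email by the iCO Smokerlyzer App to the study coordinator".
- SAP, Quality Assurance: "auto-emailed results of the CO assessment" is given as an example of the digital procedures which, taken together, are said to secure the integrity of the data.

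The participant materials describe something else. In the instructions in Protocol 15.5, "Readings will appear on your phone instantly". In the video script (15.16) the participant then answers two questions, checks or types the recipient and asks to send an e-mail; "A page will slide up displaying your email draft", and the participant must press send. The script adds: "It is very important that you complete these instructions exactly so that information from your breath tests can be shared with my digital study".

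On repeat testing, the script says: "We highly encourage you to use your Smokerlyzer throughout the study to track your progress and motivate you". Protocol 15.5 and 15.16 both say that submitting those extra values is optional.

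Protocol 10.4 and the SAP make concordance between self-reported 30-day abstinence and remote CO the secondary endpoint, with more than 85% taken as evidence of a valid reporting process.

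**The concern.** The CO reading is there to check self-report. Under the written procedure, the person being checked sees the value before deciding whether to release it. A participant who has claimed abstinence and sees a high reading could test again later and send the lower value, or send nothing. The end-of-study window is seven days (Protocol 7.10), and no rule says which reading counts if several are taken or sent. Nothing retrieves unsent readings.

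The secondary endpoint and its 85% rule are at stake, together with the SAP's stated aim of showing that reimbursement for the app can rest on remote verification. If failing readings from self-reported abstainers go missing or are replaced, concordance rises for a reason unrelated to honest reporting.

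**Working it through.** **Texts side by side.** Transmission cannot be both automatic and dependent on pressing send. The script is the operational document, and it warns that results reach the study only if its steps are followed. On the documents' own account the participant controls release. The reminder in 15.11 that follows the outcome survey asks for CO if it has not already been sent, so the reading may come before or after the survey. That leaves the endpoint reading undefined in order as well as in number.

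**Size.** The plan gives no expected concordance, number of readings or precision, so there is no figure to reproduce. The following is an illustration.

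Inputs:

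- *a*, the share of CO submitters who report 30-day abstinence. Low value: the planned rates average (26.2% + 8.3%)/2 = 17.25%; dividing by the pilot retention of 87.7% gives 0.197. High value: the pilot completer rate, 0.299. Both treat survey completers as CO submitters.
- *f*, the share of self-reported abstainers whose reading would be at or above the cut-off. Assumed, 0.10 to 0.40.
- *b*, the share of all submitters who report smoking within 30 days but read below the cut-off. Assumed, 0.10.

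Formulas, over all submitters:

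- nobody selects: 1 − af − b
- every failing abstainer withholds: (1 − af − b)/(1 − af)
- every failing abstainer retests until low: 1 − b

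| a | f | No selection | All withhold | All retest | Largest rise (points) |
|---|---|---|---|---|---|
| 0.197 | 0.10 | 88.0% | 89.8% | 90.0% | 2.0 |
| 0.197 | 0.20 | 86.1% | 89.6% | 90.0% | 3.9 |
| 0.197 | 0.30 | 84.1% | 89.4% | 90.0% | 5.9 |
| 0.197 | 0.40 | 82.1% | 89.1% | 90.0% | 7.9 |
| 0.299 | 0.10 | 87.0% | 89.7% | 90.0% | 3.0 |
| 0.299 | 0.20 | 84.0% | 89.4% | 90.0% | 6.0 |
| 0.299 | 0.30 | 81.0% | 89.0% | 90.0% | 9.0 |
| 0.299 | 0.40 | 78.0% | 88.6% | 90.0% | 12.0 |

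The rise under full retesting equals *af*, whatever *b* is. These are upper bounds: every failing abstainer selects, and no submission is protected by video.

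**Effect on the 85% rule.** Full retesting turns a fail into a pass only when af + b is 0.15 or more while b is below 0.15. At b = 0.10 that means af of at least 0.05: f of about 0.25 (0.05/0.197) or 0.17 (0.05/0.299). If b were as large as the pilot completers' gap between 7-day and 30-day abstinence, 51.5% − 29.9% = 21.6%, concordance could not exceed 1 − 0.216 = 78.4% and the rule would fail regardless. If b were 0, the lowest unselected value would be 1 − 0.299 × 0.40 = 88.0%, which already passes.

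**Who is affected.** At planned rates, self-reported abstainers number 78 × 0.262 + 78 × 0.083 = 26.9, about 27 of 156. With f from 0.10 to 0.40, that is about 3 to 11 people.

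**Denominator.** The plan does not say whether concordance is over all submitters or over self-reported abstainers only. In the latter case, full selection moves it from 1 − f, that is 90% to 60%, up to 100%.

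**The case against.** The strongest reply is that the documents show an opportunity and nothing more. Participants have no financial reason to use it: Protocol 8.2 pays $50 for submitting a CO reading, and the Day 53 message in 15.10 says payment does not depend on quit status. The reimbursement that the SAP discusses is for the app. The SAP also does not rest CO validity on automatic e-mailing alone. Its integrity statement covers the digital procedures as a whole, and it names live video for a subsample as the safeguard for CO, with monitored and unmonitored concordance then compared.

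Much of this stands. A reader might infer that concordance is in fact inflated; the documents do not support that. A reader might also infer that every unmonitored reading is biased upward. That is wrong too: upward bias needs a false claim of abstinence, and someone who reports smoking and sends a selected low value creates discordance.

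The safeguards are nevertheless partial. Payment for any value discourages withholding but does nothing against retesting. The video group is at most 25 volunteers per arm who schedule their own call and could test privately beforehand. The comparison has no stated test, margin or power, and Protocol 2.2 would take the absence of a significant difference as demonstrating validity.

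**Conclusion.** The contradiction is real and stands in the current text of both documents: the plan claims automatic transmission for a secondary endpoint, and its own participant procedure does not provide it. Unmonitored readings can be retested or withheld, which may bias concordance upward among self-reported abstainers by an unknown amount. Over all submitters the upper bound is about 2 to 12 points, resting on the assumed failure rates of 10-40%; the 10% low-reading share sets the level of concordance and whether 85% is crossed. With no selection the bias is zero.

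A reader might also infer that the main efficacy result is compromised. Protocol 8.3 and 10.3 and the SAP define the primary endpoint by self-report, so that analysis is unaffected. Only Protocol 3.1 describes the primary outcome as CO-confirmed, and selection would matter only under that reading. The change should be made, but the issue concerns a secondary endpoint.

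**What to change.** 1. In Protocol 8.3 and 11.1 and the SAP's Data Acquisition and Quality Assurance text, say that readings are sent by the participant after being seen. Remove automatic e-mailing as a ground for data integrity.
2. Define the endpoint as the first valid breath test in the Day 53-59 window, whether before or after the outcome survey, which fits the 15.11 reminder. State in Protocol 6.2 and 8.2, the Day 53/56 messages and the video script that it must be sent whatever its value.
3. If several readings arrive in the window, use the earliest.
4. Report missing CO by self-report status, and add a sensitivity analysis that counts missing CO among self-reported abstainers as discordant. If only failing abstainers withhold, this returns 1 − af − b, the unselected value; if others are also missing, it is conservative. State the denominator of the concordance rate.

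The cost is wording in the protocol, SAP and participant materials, one table and one sensitivity analysis. The limits should be stated: a participant can still hold back a first reading and send a later one, which neither the earliest-received rule nor the sensitivity analysis detects. Unmonitored concordance should therefore be reported as based on participant-selected readings. The sensitivity analysis may give a less favourable figure.

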## **15.17 Advertisement Script**

Advertisement content to be posted on Facebook, LinkedIn, Google+, and Instagram, and mailed to potential participants in a Magellan Health Care value-based care network.

Ads will include reference to a web link [LINK] that will bring participants to the Eligibility Questionnaire (see Appendix 15.2).

Sample Ad 1: Want to quit smoking? Want to earn money in the process? Sign up to join an 8-week research study evaluating 2 different smoking cessation apps that could help you break up with nicotine for good! Developed by doctors, scientists, and engineers, these apps will help you develop a smoking cessation plan complete with strategies for overcoming cravings and helpful ways to deal with withdrawal symptoms. You can earn up to \$150 for using your iPhone or Android to quit smoking, and you’ll never be asked to visit a study site. Join now! Go to [LINK] to see if you are eligible.

Sample Ad 2: Want to quit smoking and earn up to \$150 doing it? We are looking for smokers to join a research study evaluating 2 different smoking cessation apps to help you quit. Developed by doctors, scientists and engineers, these apps have helped many quit smoking already. Space is limited. Visit [LINK] to see if you are eligible and to sign up now.

Sample Ad 3: Want to quit smoking? Want to earn \$150 in the process? We are evaluating 2 different smoking cessation apps that could help you break up with nicotine for good! Developed by doctors, scientists, and engineers, these apps will help you develop a customized smoking cessation plan, complete with strategies for overcoming cravings and helpful ways to deal with withdrawal symptoms. Sign up today to join a remote (you’ll never be asked to visit a study site!) 8-week, IRB-approved research study! Go to [LINK] to see if you are eligible.

Sample Ad 4: Sign up to join an 8-week, IRB-approved research study of 2 different smoking cessation apps that you can download on your iPhone or Android. Based on scientific research

and developed by doctors, scientists, and engineers, these apps will help you develop a smoking cessation plan, complete with strategies for overcoming cravings and helpful ways to deal with withdrawal symptoms. Join this 8-week, remote (you'll never be asked to visit a study site!) study today to quit smoking and earn up to \$150 in the process. Go to [LINK] to see if you are eligible.

Sample Ad 5: Want to quit smoking? Want to earn \$150 in the process? Join this 8-week, remote research study evaluating 2 different smoking cessation apps to help you break up with nicotine for good. Go to [LINK] to see if you are eligible.

## 15.18

## Advertisements

### Want to Quit Smoking?

Want to earn \$150 in the process?

We are evaluating  
**2 different smoking**  
**cessation apps** that could  
help you break up with  
nicotine for good!

Developed by **doctors,**  
**scientists, and engineers,**  
these apps will help you  
develop a customized smoking  
cessation plan, complete with  
strategies for overcoming  
cravings and helpful ways to  
deal with withdrawal  
symptoms.

Sign up today to join a remote  
(you'll never be asked to visit a study site!)  
**8-week, IRB-approved research study!**

Go to  
<http://www.mydigitalstudy.com/g537/k3>  
to see if you are eligible.

**Want to Quit Smoking?**  
You can earn up to  
**\$150!**

Go to <http://www.mydigitalstudy.com/g537/k3> to see if you are eligible

## Want to Quit Smoking?

Want to earn \$150 in the process?

We are evaluating  
**2 different smoking  
cessation apps** that could  
help you break up with  
nicotine for good!

Developed by **doctors,  
scientists, and engineers**,  
these apps will help you  
develop a customized smoking  
cessation plan, complete with  
strategies for overcoming  
cravings and helpful ways to  
deal with withdrawal  
symptoms.

Sign up today to join a remote  
(you'll never be asked to visit a study site)  
**8-week, IRB-approved research study!**

Go to  
<http://www.mydigitalstudy.com/g537/49>  
to see if you are eligible.

## To Get Started

1. Download the **Smokerlyzer app** on the AppStore or Google play store
2. Enter the **pin code** on your Smokerlyzer and the prompted information into the app

**Smokerlyzer instructions for use:**

1. Plug the white cord into the Smokerlyzer and into your phone's headphone jack
2. Take a deep breath and hold it for 15 seconds
3. Exhale into the Smokerlyzer
4. Readings will appear on your phone instantly
5. Results will be explained and charted

## 16. MEDICAL MONITORING

### Medical Monitoring Form

To be completed by the Medical Monitor upon participant report of an adverse event via the email reporting system.

**Participant ID:**

**Description of the event:**

**Onset date:**

**Offset date:**

**Treatment required:**

**Resolution (select one):**

**Resolved completely**

**Partially resolved**

**Ongoing**

**Medical Monitor Designation (select one from each section):**

**Adverse Event**

**Serious Adverse Event**

**Suspected Unexpected Serious Adverse Reaction**

**None of the above**

**Associated/related to study intervention**

**OR**

**Not associated/related to study intervention**

10. STATISTICAL CONSIDERATIONS

10.1 General Considerations

All study analyses will be conducted after the study database is locked. All analyses will be performed on the intent-to-treat (ITT) population.

10.2 Analysis Populations

Intent to Treat (ITT) population

All participants randomized to a study app that are able to confirm download of installed treatment arm app via telephone on the randomization date will be included in the ITT cohort.

10.3 Primary Endpoint

The primary endpoint will be self-reported 30-day abstinence from smoking on the outcome survey as per Russell Standard Self- Reported 4-Week Quitter status.

30-day smoking cessation status (dichotomous variable: yes/no) will be compared between the CKT and QuitGuide groups utilizing logistic regression. Two-sided p-values will be calculated from logistic regression models, with adjustments to the models by: race, education, nicotine dependence, and living with a partner who smokes, consistent with previous studies' models.

10.4 Secondary Endpoint

Concordance rates between self-reported 30-day abstinence and the remote CO monitoring result will be estimated, with concordance > 85% considered evidence of a valid reporting process by Magellan Behavioral Health. Concordance rates will be compared between users that submit the CO measurement under video monitoring and those that do not. Upon completion of the Outcome Survey, participants will be invited to submit the CO assessment over a live video feed to confirm identity, until videos are received from 25 CKT users and 25 QG users. After 25 videos are received from each group, participants will no longer be invited to submit the CO assessment over live video feed.

Secondary analysis of the subgroup of NRT/pharmacotherapy users will be conducted to compare cessation rates between the CKT+NRT group and the CKT-only group, to confirm the initial trial result that CKT+NRT is not superior to CKT-alone.

